7.4.3 Criteria to Resume Treatment

Participants may resume treatment with study drug if they have completed AE management (ie, corticosteroid taper) or are on \leq 10 mg prednisone or equivalent, and meet the requirements per [Table 7.4.2-1](#).

Prior to re-initiating treatment in a participant with a dosing delay as defined below, the Medical Monitor must be consulted.

- For Arm A, dosing delay $>$ 6 weeks.
- For Arm B, dosing delay $>$ 6 weeks (Cycles 1 to 4) and $>$ 10 weeks (Cycles 5 to 13).

Continue tumor surveillance per protocol even if dosing is delayed. Continue periodic study visits to assess safety and laboratory studies every 4 weeks or more frequently if clinically indicated during such dosing delays.

Participants with SARS-CoV-2 infection (either confirmed or suspected) may resume treatment after **all of the following**:

- At least 10 days (20 days for severe/critical illness) have passed since symptoms first appeared or positive test result (eg, RT-PCR or viral antigen)
- Resolution of acute symptoms (including at least 24 hours has passed since last fever without fever reducing medications)
- Evaluation by the investigator with confirmation that there are no sequelae that would place the participant at a higher risk of receiving investigational treatment
- Consultation by the Medical Monitor/designee. For suspected cases, treatment may also resume if SARS-CoV-2 infection is ruled-out and other criteria to resume treatment are met.

For additional criteria to resume treatment for dosing of [REDACTED] in the [REDACTED] setting, please refer to [Appendix 5](#).

7.4.4 Management Algorithms for Nivolumab

Immuno-oncology (IO) agents are associated with AEs that can differ in severity and duration from AEs caused by other therapeutic classes. Nivolumab is considered an IO agent and the management algorithms in [Appendix 7](#) provide guidance on assessing and managing the following groups of AEs:

- Gastrointestinal
- Renal
- Pulmonary
- Hepatic
- Endocrinopathy
- Skin

- Neurological
- Myocarditis

7.4.5 Treatment of Related Infusion- and Injection-Reactions

7.4.5.1 Systemic Reactions Occurring In-clinic

Since nivolumab contains only human immunoglobulin protein sequences, systemic hypersensitivity (allergic) reactions are unlikely. Although rare, if severe hypersensitivity were to occur, common manifestations might include fever, chills, rigors, headache, rash, pruritus, arthralgias, hypotension, hypertension, and/or bronchospasm. Report all Grade 3 or 4 hypersensitivity reactions within 24 hours as an SAE.

Treatment recommendations are provided below based on CTCAE v5 grading definitions and may be modified based on local treatment standards and guidelines, as appropriate:

For Grade 1 symptoms (mild reaction; infusion/injection interruption not indicated; intervention not indicated):

- Remain at bedside and monitor participant until recovery from symptoms. The following prophylactic premedications are recommended for future infusions and injections: diphenhydramine 50 mg (or equivalent) and/or acetaminophen/paracetamol 325 to 1000 mg at least 30 minutes before additional nivolumab administrations.

For Grade 2 symptoms: (Therapy or infusion interruption indicated but responds promptly to symptomatic treatment (eg, antihistamines, NSAIDS, narcotics, IV fluids); prophylactic medications indicated for ≤ 24 hours):

- Stop the study drug infusion/injection. Begin an IV infusion of normal saline and treat the participant with diphenhydramine 50 mg IV (or equivalent) and/or acetaminophen/paracetamol 325 to 1000 mg; remain at bedside and monitor participant until resolution of symptoms. Corticosteroid and/or bronchodilator therapy may also be administered as appropriate. For the participants receiving Nivo IV, if the infusion is interrupted, then restart the infusion at 50% of the original infusion rate when symptoms resolve; if no further complications ensue after 30 minutes, the rate may be increased to 100% of the original infusion rate. Monitor participant closely. If symptoms recur, then no further study medication will be administered at that visit.
- For participants in Arm A (Nivo SC) who need to receive 2 sequential injections for a full dose, do not administer the second injection if symptoms are noted with the first injection, and follow the treatment instructions mentioned above.
- For future infusions or injections, the following prophylactic premedications are recommended: diphenhydramine 50 mg (or equivalent) and/or acetaminophen/paracetamol 325 to 1000 mg administered at least 30 minutes before nivolumab infusions or injections. If necessary, corticosteroids (up to 25 mg of hydrocortisone or equivalent) may be used.

For Grade 3 or 4 symptoms: (severe reaction, Grade 3: Prolonged (eg, not rapidly responsive to symptomatic medication and/or brief interruption of infusion); recurrence of symptoms following initial improvement; hospitalization indicated for clinical sequelae. Grade 4: Life-threatening consequences; urgent intervention indicated):

- Immediately discontinue infusion/injection of study drug. Begin an IV infusion of normal saline and treat the participant as follows: Recommend bronchodilators, epinephrine 0.2 to 1 mg of a 1:1000 solution for subcutaneous or intramuscular administration or 0.1 to 0.25 mg of a 1:10,000 solution injected slowly for IV administration, and/or diphenhydramine 50 mg IV with methylprednisolone 100 mg IV (or equivalent), as needed. Monitor participant until the investigator judges that the symptoms will not recur. Study drug will be permanently discontinued. Follow institutional guidelines for the treatment of anaphylaxis. Remain at bedside and monitor participant until recovery of the symptoms.
- For participants in the Nivo SC arm (Arm A) who need to receive 2 sequential injections for a full dose, do not administer the second injection if symptoms are noted with the first injection, and follow the treatment instructions mentioned above.

7.4.5.3 Management of Local Infusion or Injection Site Reactions

In the clinical experience with Nivo IV, no tissue necrosis has been observed after accidental extravasations of Nivo IV. The use of oral medications (eg, antihistamines, acetaminophen/paracetamol) and topically applied therapies such as cold packs and steroid or antihistamine creams or gels is allowed for the treatment of local injection reactions due to Nivo SC [REDACTED] (eg, swelling, erythema, pain, induration, local pruritus) and infusion local site reactions (local inflammation, necrosis due to drug extravasation) including those related to procedures (eg, hematoma). Local/institutional guidelines, if available, can be followed.

In case of late-occurring hypersensitivity symptoms (eg, appearance of a localized or generalized pruritus within 1 week after treatment), symptomatic treatment may be given (eg, oral antihistamine or corticosteroids).

7.5 Preparation/Handling/Storage/Accountability

Refer to the current version of the BMS-936558 IB for Nivo IV, the BMS-986298 IB for Nivo SC [REDACTED] and the Pharmacy Manual for complete information on storage, handling, dispensing, and administration information.

The IP/AxMP must be stored in a secure area according to local regulations. It is the responsibility of the investigator, or designee where permitted, to ensure that IP/AxMP is only dispensed to study participants. The IP/AxMP must be dispensed only from official study sites by authorized personnel according to local regulations.

The product storage manager should ensure that the study intervention is stored in accordance with the environmental conditions (temperature, light, and humidity) as determined by BMS. If concerns regarding the quality or appearance of the study intervention arise, the study intervention should not be dispensed, and BMS should be contacted immediately.

Study intervention not supplied by BMS will be stored in accordance with the package insert.

IP/AxMP documentation (whether supplied by BMS or not) must be maintained that includes all processes required to ensure the drug is accurately administered. This includes documentation of drug storage, administration and, as applicable, storage temperatures, reconstitution, and use of required processes (eg, required diluents, administration sets).

- The investigator or designee must confirm appropriate temperature conditions have been maintained during transit for all study intervention received and any discrepancies are reported and resolved before use of the study intervention.
- The investigator, institution, or the head of the medical institution (where applicable) is responsible for study intervention accountability, reconciliation, and record maintenance (ie, receipt, reconciliation, and final disposition records).
- Further guidance and information for the final disposition of unused study interventions are provided in [Appendix 2](#).

7.5.1 Retained Samples for Bioavailability/Bioequivalence/Biocomparability

At the time of receipt of the IP by the investigator or designee, BMS will specify the appropriate number of containers or units to select for retention, the conditions of sample storage, required duration of sample retention, and provisions for returning or disposing of the IP. When samples are selected, containers or units should be placed in packaging with a tamper-evident seal provided by BMS or sourced by the site. Package labeling should clearly identify the contents as retention samples and state that the IP should be stored in the restricted area with limited access.

Additional details regarding the retention process will be provided in a Pharmacy Manual or other written documentation.

7.6 Treatment Compliance

Study intervention compliance will be periodically monitored by drug accountability as well as the participant's medical record and CRF. Drug accountability should be reviewed by the site study

staff at each in-clinic visit to confirm treatment compliance. Sites should discuss discrepancies with the participant at each on-treatment study visit.

In addition, should the site identify a potential out-of-window dosing, the site must reach out to the participant and provide guidance on dosing, to be determined on a case-by-case basis (eg, to proceed immediately with dose, wait until the next dosing cycle, or delay the dose and resume treatment per investigator assessment).

A record of the quantity of [REDACTED] dispensed to and administered by each participant must be maintained and reconciled with study intervention and compliance records. Intervention start and stop dates, including dates for intervention delays, will also be recorded in the CRF (in-clinic dosings) [REDACTED]

7.7 Concomitant Therapy

7.7.1 Prohibited and/or Restricted Treatments

Prohibited and/or restricted medications taken prior to study treatment administration are described below. Medications taken within 30 days prior to the first dose of study treatment must be recorded on the CRF.

The following medications and treatments are prohibited during the study (unless utilized to treat a drug-related adverse event).

- Immunosuppressive agents.
- Immunosuppressive doses of systemic corticosteroids. Participants are permitted the use of topical, ocular, intra-articular, intranasal, and inhalational corticosteroids (with minimal systemic absorption). Adrenal replacement steroid doses > 10 mg daily prednisone are permitted. A brief (less than 3 weeks) course of corticosteroids for prophylaxis (eg, contrast dye allergy) or for treatment of non-autoimmune conditions (eg, delayed-type hypersensitivity reaction caused by a contact allergen) is permitted.
- Any concurrent systemic anti-neoplastic therapy, including any concurrent adjuvant therapy for melanoma or for a new malignancy. Participants who develop a new non-melanoma fully resectable malignancy (examples include but are not limited to in situ bladder cancer, in situ gastric cancer, or in situ colon cancers; in situ cervical cancers/dysplasia; or breast carcinoma in situ; or prostate carcinoma) during the study may continue receiving study drugs if the only therapy required is hormonal therapy, surgery, and/or radiation (and the surgery or radiation site does not overlap with a previous primary melanoma or melanoma metastasis location). Consultation with the Medical Monitor is required once a new malignancy is detected.
- Any complementary medications (eg herbal supplements or traditional Chinese medicines) intended to treat the disease under study. Such medications are permitted if they are used as supportive care.

- Any live attenuated vaccine (eg, live COVID-19 vaccines, varicella, zoster, yellow fever, rotavirus, oral polio and measles, mumps, rubella [MMR]) during treatment and until 100 days post last dose.
 - COVID-19 vaccines that are NOT live are permitted prior to study, during the study, and after the last dose of nivolumab. Please contact the medical monitor with any questions related to COVID-19 vaccines.
 - ◆ The following are NOT considered live vaccines and the decision to vaccinate should be made by the investigator and participant: inactivated vaccines (eg, heat-killed and formalin-killed vaccines), subunit vaccines, toxoid vaccines, nucleic acid vaccines that do not encode potentially infectious virus (Pfizer/BioNTech and Moderna COVID-19 vaccines) and replication-incompetent recombinant vector vaccines. If a study participant has received a live COVID-19 vaccine prior to screening, enrollment should be delayed until the impact of the vaccine is stabilized, UNLESS a delay would compromise participant health, as determined by the investigator in consultation with medical monitor. For COVID-19 vaccines requiring more than a single dose, the full series (eg, both doses of a 2-dose series) should be completed prior to enrollment when feasible, and when a delay in enrollment would not put the study participant at risk. Ideally, enrollment would occur after any acute reactions (eg, reactions occurring within 24 hours of vaccine administration) resolve.

Supportive care for disease-related symptoms may be offered to all participants on the trial.

7.7.2 *Other Restrictions and Precautions*

Participants are prohibited from joining another clinical trial while they are participating in this study.

7.7.2.1 *Imaging Restriction and Precautions*

It is the local imaging facility's responsibility to determine, based on participant attributes (eg, allergy history, diabetic history, and renal status), the appropriate imaging modality and contrast regimen per imaging study. Imaging contraindications and contrast risks are to be considered in this assessment. Participants with renal insufficiency are to be assessed as to whether or not they should receive contrast and if so, which contrast agent and dose is appropriate. Specific to MRI, participants with severe renal insufficiency (ie, estimated glomerular filtration rate [eGFR] < 30 mL/min/1.73 m²) are at increased risk of nephrogenic systemic fibrosis, therefore MRI contrast is contraindicated. In addition, participants may be excluded from MRI if they have tattoos, metallic implants, pacemakers, etc. This will be outlined in the image manual.

Gentle hydration before and after IV contrast should follow local standard of care. The ultimate decision to perform MRI in an individual participant in this study rests with the site radiologist, the investigator, and standards set by the local Ethics Committee.

7.8 Continued Access to Study Intervention After the End of the Study

At the end of the study, BMS will not continue to provide BMS-supplied study intervention to participants/investigators unless BMS chooses to extend the study. The investigator should ensure that the participant receives appropriate standard of care to treat the condition under study.

8 DISCONTINUATION CRITERIA

8.1 Discontinuation From Study Intervention

Participants MUST discontinue IP (and Non-IP/AxMP at the discretion of the investigator) for any of the following reasons:

- Participant's request to stop study intervention. Participants who request to discontinue study intervention will remain in the study and must continue to be followed for protocol-specified follow-up procedures. The only exception to this is when a participant specifically withdraws consent for any further contact with him/her or persons previously authorized by the participant to provide this information
- Any clinical AE, laboratory abnormality, or intercurrent illness which, in the opinion of the investigator, indicates that continued participation in the study is not in the best interest of the participant
- Termination of the study by BMS
- Loss of ability to freely provide consent through imprisonment or involuntarily incarceration for treatment of either a psychiatric or physical (eg, infectious disease) illness. (Note: Under specific circumstances and only in countries where local regulations permit, a participant who has been imprisoned may be permitted to continue as a participant. Strict conditions apply, and BMS approval is required.)
- Disease recurrence (local, regional, or distant)
- Additional protocol-specified reasons for discontinuation ([Section 8.1.1](#))
- Pregnancy (refer to [Section 9.2.5](#))
- Significant noncompliance with protocol (eg, procedures, assessments, medications, etc.). The investigator should discuss such issues with the Medical Monitor.

Refer to the Schedule of Activities for data to be collected at the time of treatment discontinuation and follow-up and for any further evaluations that can be completed.

All participants who discontinue study intervention should comply with protocol-specified follow-up procedures as outlined in [Section 2](#). The only exception to this requirement is when a participant withdraws consent for all study procedures, including post-treatment study follow-up, or loses the ability to consent freely (eg, is imprisoned or involuntarily incarcerated for the treatment of either a psychiatric or physical illness).

If study intervention is discontinued prior to the participant's completion of the study, the reason for the discontinuation must be documented in the participant's medical records per local regulatory requirements in each region/country and entered on the appropriate CRF page.

8.1.1 *Nivolumab Discontinuation*

Nivolumab treatment must be permanently discontinued per criteria in [Table 7.4.2-1](#) in [Section 7.4](#). Discontinue nivolumab for any adverse event, laboratory abnormality, or intercurrent illness which, in the judgment of the investigator, presents a substantial clinical risk to the participant with continued nivolumab dosing.

Any event that leads to delay in dosing from the previous dose as described in [Section 7.4.3](#) requires discontinuation of study treatment, with the following exceptions:

- Dosing delays to allow for prolonged steroid tapers to manage drug-related adverse events are allowed.
- Dosing delays lasting longer than those described in [Section 7.4.3](#) that occur for non-drug-related reasons may be allowed if approved by the Medical Monitor (or designee).

8.1.2 *Post-study Intervention Study Follow-up*

Per Protocol Amendment 01, survival follow-up is not required. Participants will be followed for assessment of safety through 100 days (\pm 7 days) after the last dose of study treatment. Participants will not be followed for survival.

The following information refers to the original study design: In this study, overall survival is a key endpoint of the study. Post-study follow-up is of critical importance and is essential to preserving participant safety and the integrity of the study. Participants who discontinue study intervention must continue to be followed (in this study or a rollover study) for collection of outcome as required and in line with [Section 5](#) until death or the conclusion of the study.

BMS may request that survival data be collected on all treated/randomized/assigned participants outside of the protocol defined window as defined in [Section 2](#). At the time of this request, each participant will be contacted to determine their survival status unless the participant has withdrawn consent for all contact or is lost to follow-up.

Participants who discontinue study intervention may continue to be followed.

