3.1 Study Rationale

Overall Rationale for Protocol Amendment 01

BMS has made a strategic decision to terminate the CA2096GE trial. This decision was not related to any safety concerns. Study recruitment has closed and treatment of ongoing, active participants will continue per Protocol Amendment 01. Changes implemented in this amendment aim to alleviate participant and site burden and include updates to sample collection, study procedures, and study design.

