5 STUDY DESIGN

5.1 Overall Design

Study CA2096GE is a multicenter, open-label, Phase 3 study. **Per Protocol Amendment 01, PK co-primary endpoints, secondary endpoints, [REDACTED] of the study have been removed. Efficacy, PROs, and biomarker analyses will not be completed. Samples already collected for PK and immunogenicity assessments will be analyzed bioanalytically for nivolumab concentrations and ADAs and reported as listings. Further collections for PK, ADAs, biomarkers, and PROs will be discontinued. Only safety assessments will be conducted.** Therefore, the study design has been adapted to reflect the Protocol Amendment 01 changes, [REDACTED]. Part 1 is no longer hypothesis-driven, but rather descriptive in nature (Arm A and Arm B), with the primary objective being safety and tolerability and exploratory objective as described in [Table 4-1](#).

- Arm A (n = 6):

- [REDACTED]

[figure not shown]
- Arm B (n = 8):

- Nivo IV (BMS-936558) 240 mg Q2W for Cycles 1 through 4.
 - Nivo IV 480 mg Q4W Cycle 5 onwards for up to total of 52 weeks.
 - All dosing will be performed in-clinic.

Participants will be stratified by stage (Stage IIIA/B vs Stage IIIC/D/IV) per AJCC 8th edition [REDACTED]

All participants will be treated until recurrence of disease, unacceptable toxicity, participant withdrawal of consent, death, or a maximum of 52 weeks of treatment from first dose, whichever occurs first.

The study design schema is presented in [Figure 5.1-1](#).

Figure 5.1-1: Study Design Schema

Abbreviations: AJCC, American Joint Committee on Cancer; CNS, central nervous system; FU, follow-up; IV, intravenous; N, number of participants; Nivo, nivolumab; PK, pharmacokinetic, Q2W, every 2 weeks; Q4W, every 4 weeks; RT, radiation therapy; SC, subcutaneous; vs, versus.

^a Treatment until recurrence of disease, unacceptable toxicity, participant withdrawal of consent, death, or a maximum of 52 weeks of treatment from first dose, whichever occurs first.

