5.1.4 Data Monitoring Committee and Other Committees

Data Monitoring Committee: A safety DMC will be implemented in this study to provide safety oversight throughout the course of Part 1 of the study. The DMC charter will describe the procedures related to the committee operations in greater detail. On 26-Oct-2022, enrollment was paused and a total of 14 participants had been randomized. On 24-Feb-2023, the study was terminated with no additional participants having been randomized. As this is an open-label study, the Sponsor will continue the safety monitoring of remaining participants in the study. No subsequent DMC meeting will occur.

Study Steering Committee: A Study Steering Committee (SSC) will be established to provide advisory oversight of the quality of the trial, with the objective of ensuring scientific integrity and the successful conduct of the CA2096GE Study. On 26-Oct-2022, enrollment was paused and a total of 14 participants had been randomized. On 24-Feb-2023, the study was terminated with no additional participants having been randomized. The Sponsor will continue to ensure the scientific integrity and successful conduct of the study. No SSC meeting will occur.

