5.2 Number of Participants

The trial has been terminated. [REDACTED] 14 participants randomized and treated in the study with 6 participants in Arm A and 8 participants in Arm B.

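### Does the mandatory stop for study termination in Section 8.1 contradict continued treatment under Protocol Amendment 01?

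*Combined protocol and SAP*

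**What the plan says.** Section 8.1 opens its list with "Participants MUST discontinue IP (and Non-IP/AxMP at the discretion of the investigator) for any of the following reasons". One item reads "Termination of the study by BMS". It has no qualifier, does not define termination, and carries no label marking it as inapplicable under Protocol Amendment 01.

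Elsewhere the amended text treats termination as past. Section 5.1.4 says "On 24-Feb-2023, the study was terminated with no additional participants having been randomized", and the protocol summary (Section 1) repeats this. Section 5.2 says "The trial has been terminated".

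On what happens to people still on treatment, Section 3.1 says "Study recruitment has closed and treatment of ongoing, active participants will continue per Protocol Amendment 01", and the summary says the same. Section 5.1 gives the duration rule: "All participants will be treated until recurrence of disease, unacceptable toxicity, participant withdrawal of consent, death, or a maximum of 52 weeks". Study termination is not among its stopping reasons.

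**The concern.** The Section 8.1 list is mandatory, and one of its triggers appears from other sections to have been met already. A literal reader would conclude that every remaining participant had to come off study drug. A reader of Sections 3.1 and 5.1 would keep them on it for up to 52 weeks.

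If sites acted on different readings, three things could diverge: the exposure behind the safety tables, the reason for discontinuation that Section 8.1 requires on the case report form, and the calendar dates covered by adverse event collection. Safety is the only primary endpoint left (Section 10.4.2), so a real ambiguity about when treatment ends would deserve attention.

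**Working it through.** The plan gives no figure to reproduce. The check compares the text and then bounds how much treatment could be affected.

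**Text comparison**

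| Place | What it implies about dosing after the decision to terminate |
|---|---|
| Section 8.1 bullet | Stop, if the trigger is the February 2023 event |
| Sections 1 and 3.1 | Continue; stated in the same paragraph as the decision to terminate |
| Section 5.1 duration rule | Continue to 52 weeks unless another listed reason applies |
| Tables 2-2 and 2-3 | Current dosing and visit schedules, to Cycle 13 in Arm A and for all later cycles in Arm B |
| Section 7.1.1 | IV dosing until, among other limits, the end of the study |
| Section 5.1.4 | Sponsor continues safety monitoring of the participants who remain |
| Section 10.4.6.3 | Database lock about 100 days after the last participant's last treatment |

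Only the first row points to stopping, and only if its wording is tied to the February 2023 event. A narrower sense is available. Sections 6.1 and 6.2 give 24-Feb-2023 as the date by which enrollment had closed. Section 5.3 places the end of the trial at the last participant's last visit or Follow-up Visit 2. Section 7.8 ties the sponsor's drug supply to the end of the study. The bullet can therefore be read as the sponsor actually ending the study, although the document does not say so.

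**Bound on the treatment affected**

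Inputs:
- Section 5.1.4: "On 26-Oct-2022, enrollment was paused and a total of 14 participants had been randomized".
- Section 7.1.1 and Table 2-1: first dose within 3 calendar days of randomization.
- Table 7.1-1: Arm B has 8 doses every 2 weeks, then 9 every 4 weeks, so 8 + 9 = 17.
- Table 2-2: Arm A is dosed every 2 weeks over 13 cycles of 28 days, so 13 × 2 = 26.
- Document history: the amendment is dated 25-May-2023.

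Latest possible first dose: 26-Oct-2022 + 3 days = 29-Oct-2022.

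Days from then to 25-May-2023: 2 (October) + 30 + 31 + 31 + 28 + 31 + 30 + 25 = 208.

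Scheduled doses by that date, with no delays:
- Arm A: floor(208/14) + 1 = 14 + 1 = 15; remaining 26 − 15 = 11.
- Arm B: 8 doses on days 0 to 98, then doses on days 112, 140, 168 and 196, so 8 + 4 = 12; remaining 17 − 12 = 5.

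Remaining time to 52 weeks: 364 − 208 = 156 days.

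These are upper bounds per participant. The documents say only that 14 people had been randomized when enrollment paused. They do not say that the last was randomized that day, or how many were still on drug in May 2023. Earlier randomization lowers the counts. A count from 24-Feb-2023 would not bear on this text, because the protocol version in force then is not supplied.

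**Effect on the analysis**

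Section 10.4.2 counts the 30-day and 100-day windows from the last dose received. A participant who stops early and one who completes 52 weeks are handled by the same definition, so neither reading changes the rule. Sections 3.1.1 and 5.1 state that no hypothesis is tested and that the study is descriptive, with 6 participants in Arm A and 8 in Arm B.

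**The case for a change.** The strongest case for acting is that Section 8.1 is operative. The amendment marks many sections as no longer applicable and updated Section 8.1.2 nearby, yet left this bullet alone. Termination is an undefined word, distinct from the defined end of trial, and Sections 5.1.4 and 5.2 use it in the past tense for the February 2023 event. Section 9 allows no waivers, so continued dosing breaks a mandatory rule on its face. One sentence would settle the matter.

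The literal conflict stands, and so does the point that the reader must supply the distinction between termination and end of study. The consequence does not stand. The provision addressed to this particular termination says that treatment continues, and it is stated alongside the announcement of termination itself. Dosing under an approved amendment that provides for it is not a waiver. For exposure or the discontinuation data to differ, a site would have to stop all its participants on the strength of a generic bullet in an amendment whose schedules describe their further dosing. The documents give no sign of that. With 14 participants, any such stop should also be recognizable from the recorded discontinuation reasons.

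**Conclusion.** The wording is inconsistent, but the inconsistency is clerical and no change to the design or analysis follows. Section 8.1 conflicts on its face with Sections 1, 3.1, 5.1.4 and 5.2, and the passages need to be reconciled editorially by saying which termination event the bullet means. That would not alter the safety windows, the tabulations or any conclusion the study can draw.

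The most that could be in play at the amendment date is 11 Arm A doses or 5 Arm B doses for any one participant. This assumes randomization on 26-Oct-2022, first dose three days later and no delays.

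The conclusion rests on two assumptions: that sites follow the amendment's schedules and its explicit statement about ongoing participants, and that last-dose dates are recorded as they occurred. It takes no position on which treatment rule is right.
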